**Hypothesis for Aim 2:**

2.1 – Our primary hypothesis is that, after reaching bilirubin levels  $> 2$  mg/dL, patients receiving Omegaven® will reach a bilirubin level  $\leq 2$  mg/dL faster than patients receiving conventional fat emulsions. Additionally, while patients receiving Omegaven® will experience a decrease in their levels of bilirubin and other hepatic enzymes over time, patients receiving conventional emulsions will maintain high levels of bilirubin and other hepatic enzymes over time.

2.2 – Patients with surgical gastrointestinal disease and cholestasis will have better clinical hepatic outcomes than patients receiving conventional emulsions.

2.3 – Since patients receiving Omegaven® will have improved immune function, they will have a lower infection rate than patients receiving conventional fat emulsions.

2.4 – Due to a better general hepatic condition, patients receiving Omegaven® will also experience lower occurrence of liver transplant, death from hepatic associated causes, and blood transfusions.

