### **D. Definition of Primary and Secondary Outcomes/Endpoints**

Generally, primary safety analyses will be based on time from baseline or 30 days after baseline until two months after patients first reached direct bilirubin levels  $< 2$  mg/dL. Baseline will be defined as information collected at the date that treatment starts for Omegaven® patients and on the date that patient reached bilirubin levels  $> 2$  for soybean oil fat emulsion patients. Information on mortality and transplant will be collected during the whole treatment with Omegaven®. Primary efficacy analysis will include time from baseline until the patient normalizes bilirubin (presents three consecutive direct bilirubin  $\leq 2$  mg/dL or a direct bilirubin  $\leq 2$  mg/dL and weaned from TPN).

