## **DATA ANALYSIS PLAN**

Using graphical methods (including boxplots) and descriptive statistics, we will assess assumptions required for validity of statistical methods and presence of outliers. Continuous variables will be summarized via means (and standard deviations) or medians (and interquartile ranges, when appropriate. When appropriate, variables will be transformed.

Primary analyses of the primary outcome will be based on the intention-to-treat analysis i.e., patient will be considered receiving Omegaven® throughout the whole follow-up period, regardless of temporary discontinuation of treatment due to infections or other causes.

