#### *Analysis of Efficacy of Omegaven®*

The primary outcome to gain preliminary evidence of efficacy will be based on the time from baseline to normalization of bilirubin level, i.e., first time point among three consecutive in which bilirubin is < 2 mg/dL. We do not anticipate that any subject will present a rebound on direct bilirubin after normalization. However, we will describe the cohort with respect to the frequency of rebounds in bilirubin levels.

Time to normalize direct bilirubin levels will be estimated using Kaplan-Meier curves. We will estimate hazard ratios and adjust for potential baseline confounders using Cox-proportional hazard models. For all survival analysis based on non-parametric or semi-parametric methods, we will attribute an infinite time to event for subjects who die or receive a liver transplant before bilirubin is normalized. Subjects who die before their bilirubin levels normalize (particularly due to liver failure) have in fact the worst outcome (infinite time to normalize bilirubin) and were not censored before reaching the endpoint of interest. Results of these analyses will be compared with results of analysis excluding subjects who die or are transplanted. Time to reach a total bilirubin of 1.2 will also be estimated using survival analysis methods. Analyses of this outcome will proceed as described for direct bilirubin.

We will also describe individual profiles over time (i.e., 2 months before baseline or birth until end of follow-up period) for all subjects using graphical methods. Trends in liver function markers over time will be explored using generalized linear models in which correlations of observations within subjects will be accounted using a generalized equations or random effects approach. We will perform these analyses including only subjects who did not die or undergo transplantation and including all subjects but assigning for subjects who died or underwent a transplant their worse possible outcome after they died or had the transplant. Using descriptive statistics, we will also explore the association between spikes in blood tests over time and predictors including transfusions of red blood cell products and blood stream infections.

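### The exploratory liver-marker trends are planned in two unranked versions: one selects children by later death or transplant, the other rests on an undefined assigned value

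*Protocol*

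**What the plan says.** All of the analysis text is in the Protocol, Analysis of Efficacy of Omegaven®.

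- **Trends.** They are exploratory: "Trends in liver function markers over time will be explored using generalized linear models". Correlation within a child may be handled by estimating equations or by random effects, and the choice is left open. One sentence then gives two populations. The first is "We will perform these analyses including only subjects who did not die or undergo transplantation". The second is "including all subjects but assigning for subjects who died or underwent a transplant their worse possible outcome after they died or had the transplant". Neither is named as leading, and the worst outcome has no numerical definition for any marker.
- **Time to normalisation.** The main analysis keeps everyone: "we will attribute an infinite time to event for subjects who die or receive a liver transplant before bilirubin is normalized". Beside it stands a comparison: "Results of these analyses will be compared with results of analysis excluding subjects who die or are transplanted".
- **Hypothesis 2.1.** Its second claim is what the trends address: "patients receiving Omegaven® will experience a decrease in their levels of bilirubin and other hepatic enzymes over time".
- **Timing of the excluding events.** Section D states: "Information on mortality and transplant will be collected during the whole treatment with Omegaven". Membership of the survivors-only set is therefore settled after baseline.

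**The concern.** Whether a child belongs to the survivors-only set is known only at the end of follow-up. The Protocol itself ties the excluding events to the marker. It describes children who die before normalising as having the worst outcome, and under Potential Risks of No Treatment it gives liver failure and death as the course of the disease. Dropping these children also drops every value measured before the event. Those who remain are partly selected for improving, so their average can fall even if the drug does nothing.

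The second version does not settle the matter, because its result depends on whatever value is assigned after death or transplant. The two versions lean in opposite directions. Without a stated order, a report could lead with the favourable one. With the 20 to 30 patients considered under Statistical Power and Sample Considerations, a handful of events is enough to move the trend.

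**Working it through.** **Nothing to reproduce.** The Protocol gives no death or transplant rate, slope, variance or efficacy sample size. Table 4 concerns McNemar power for adverse events and does not bear on this point. Every input below is an assumption.

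**1. Small example.** Take 25 children. Bilirubin falls 0.5 mg/dL per month in 20 of them and rises 1.0 in the 5 who die or are transplanted.
- Survivors only: mean slope −0.5.
- All children: (20 × −0.5 + 5 × 1.0)/25 = −5/25 = −0.2 mg/dL per month.

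**2. Bias when the true mean trend is zero.** Simulation of 100,000 children per scenario over 24 weeks: SD of baseline log bilirubin 0.5, between-child slope SD 0.03 or 0.06 per week on the log scale, hazard of death or transplant proportional to current bilirubin. The 24-week change is exp(24 × mean slope) − 1.

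| Excluded | Slope SD 0.03: slope per week, change | Slope SD 0.06: slope per week, change |
|---|---|---|
| 10% | −0.0012, −2.8% | −0.0051, −11.5% |
| 20% | −0.0024, −5.5% | −0.0096, −20.6% |
| 30% | −0.0037, −8.6% | −0.0145, −29.4% |

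With all children kept, the change lies between −0.4% and +0.2%. The apparent fall among survivors comes entirely from the selection.

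**3. Sensitivity of the worst-value version.** In the example of step 1, look at month 6 and suppose all 5 events have occurred by then. The 20 survivors have changed by 6 × −0.5 = −3.0 mg/dL. Let the assigned value lie D mg/dL above baseline. The mean change is (20 × −3.0 + 5 × D)/25 = −2.4 + 0.2D, which is zero at D = 12. A smaller assigned value shows a fall and a larger one a rise, from the same children. The sign depends on a number that the Protocol does not state.

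**4. Which model for the observed values.** Same kind of simulation, slope SD 0.06, about 29% with an event, true mean slope near zero:
- survivors only: −0.014 per week, exp(24 × −0.014) − 1 = −28.5%;
- all observed values, GEE with independence working correlation: −0.015 per week, −30.2%;
- all observed values, random-effects model: −0.001 per week, −2.4%.

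Including everyone's observed values is therefore not enough. Under independence GEE, children with rising values leave the data and the later average drifts down just as it does in survivors. The random-effects model nearly removes the bias here.

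**5. Time to normalisation.** Suppose 15 of 25 normalise and 5 of the other 10 die or are transplanted. The main analysis gives 15/25 = 60%. The comparison analysis gives 15/20 = 75%. An infinite time keeps these children in the risk set without an event, which in effect is a cumulative incidence with death and transplant as competing events. As worded, the comparison analysis also removes a child who normalises first and is transplanted later.

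**The case against.** The strongest reply is that the two trend versions bracket the answer. One leans towards a decline, the other against it, and a fall seen only in survivors would be exposed by its partner. Individual profiles are also to be described for all subjects. The trends are exploratory in a study seeking preliminary efficacy, and a separate analysis plan could rank the versions and define the value. Much of this stands, and it limits how serious the point is. It does not remove it: a bracket with one arbitrary end is of little use, and the Protocol itself sets the two versions side by side without an order.

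A reader might infer three stronger things, none of which the text supports:
- **That trends are run only in survivors.** The second half of the same sentence plans an all-subject version.
- **That values measured before death or transplant are never used.** The all-subject version assigns the worst outcome only after the event, so earlier values can stay in. What is missing is a version in all children that rests on observed values alone.
- **That the primary efficacy analysis is biased, or that intention to treat is breached.** The main time-to-normalisation analysis keeps these children at infinite time. The statement "Primary analyses of the primary outcome will be based on the intention-to-treat analysis" concerns the primary outcome, and the exclusion there is only a comparison.

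It is also fair to say that using observed values alone is no cure in itself. Step 4 bears this out for independence GEE, and the fix is worded accordingly.

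**Conclusion.** The point holds for the exploratory trend analyses. One of the two planned versions conditions on a post-baseline event related to bilirubin and favours hypothesis 2.1. The other turns on an undefined value. No rule says which leads. Under the stated assumptions, the survivors-only trend shows a fall of about 3% to 29% over 24 weeks when the true mean trend is zero. The size depends on the death or transplant rate, the spread of slopes and the link between bilirubin and the event, none of which the Protocol gives. The direction was the same in all six scenarios.

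The main time-to-normalisation analysis is sound. Only the label of its comparison analysis needs attention. The trends should be reworded because they carry the second claim of hypothesis 2.1, but the primary efficacy result does not depend on them.

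**What to change.** In Analysis of Efficacy of Omegaven®:

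1. Name as the leading trend analysis a random-effects model with child-specific intercepts and slopes, in all children, using every value observed up to death or transplant. Do not use independence GEE for it. Report the number and timing of deaths and transplants beside the trend.
2. Keep the worst-value version as a sensitivity analysis, with the assigned value stated for each marker before the data are examined.
3. Label the survivors-only trend as descriptive, or drop it.
4. Leave the main time-to-normalisation analysis unchanged. Label the comparison that excludes children who die or are transplanted as descriptive only.

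**Cost.** Wording only. The withdrawal section already requires measurements up to the date of withdrawal to be documented, including withdrawal for transplant, so no new data are needed. The trends may look less favourable. The random-effects model also has a price: it assumes that the observed values account for who leaves, and its slope describes a course in the absence of death or transplant. That is why the events must be shown with it.

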## **DESIGN AND METHODS**

### **A. Study Design**

Assessment of the effect of treatment will be based on a non-randomized, open-labeled, prospective study of intravenously administered Omegaven® fat emulsion to determine safety and preliminary efficacy in the treatment of PN associated liver injury.

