### Outcome/Endpoints

#### *Treatment safety*

Our primary outcome for treatment safety will be based on patient's essential fatty acid profile. We will compare patients before treatment with Omegaven® started and after treatment started (one month after treatment started until treatment stopped) with respect to the frequency with which triene/tetraene ratio  $> 0.2$  at any time. Primary analyses for these and all other safety outcomes will be based on a follow-up time for Omegaven® starting 30 days after baseline, i.e., 30 days after treatment started for Omegaven® patients and 2 months after the first direct bilirubin level  $< 2$  mg/dL was recorded.

Additional comparisons across treatment periods for subjects receiving Omegaven® will be aimed to assess occurrence of spontaneous bleeding (e.g., unexplained bruising, oozing from gums/incision sites), and maximum triene/tetraene ratio, minimum platelets, maximum international normalized ratio (INR), and trends in pre-albumin (age standardized levels). We will also explore trends in coagulopathies based on curves of platelets, prothrombin time (PT), partial thromboplastin time (PTT) over time, and INR. We will also describe the rate with which INR ratios were  $> 2$  (number of days/follow-up time), as a marker of coagulopathies.

Additional evaluation of Omegaven® will be performed with regards to rate in which albumin is  $> 3$  g/dL, maximum triglyceride level, rate of blood stream infections (number of positive blood cultures/follow-up-time under PN after baseline), rate of central venous catheter (CVC) infections (number of CVC infections/follow-up time and number of gram positive CVC infections/follow-up time), and occurrence of anaphylactic reactions after baseline.

We will describe trends over time for all outcomes associated with fatty acid profiles (including triene/tetraene ratios, triglycerides, total omega-6 fatty acids, total omega-3 fatty acids, total saturated, total monounsaturated, and total polysaturated fatty acids). Specific fatty acids such as arachidonic, palmoleic, palmitic, oleic, stearic, and linoleic fatty acids will also be evaluated and described.

[name], Department of Surgery, Children's Hospital & Medical Center  
[name], Department of Surgery, Children's Hospital & Medical Center  
[name], Pediatric Research Office, Dept. of Pediatrics, UNMC  
[name], Department of Biostatistics, College of Public Health, UNMC

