### *Analysis of Safety and Tolerability of Omegaven®*

All primary safety and tolerability analyses will be based on descriptive statistics. In secondary analyses, we will also assess the statistical significance of differences. The period receiving Omegaven® will start 30 days after beginning PN with Omegaven® for the main analysis. Outcomes measured in the Omegaven® will be described for a period starting 30 days after baseline.

Primary outcomes measured will include whether the triene/tetraene ratio was ever  $> 0.2$  during the intervention period and whether the INR was ever  $> 2$ . Secondary outcomes measured will include platelets, prothrombin time (PT), partial thromboplastin time (PTT), and other components of the fatty acid profile. Analysis of all categorical outcomes will be based on proportions and of all continuous outcomes will be based on means or medians of the individual mean, maximum or minimum values, as appropriate, during the respective follow-up period. Comparisons between periods (pre and post-treatment) will be performed based on paired tests, parametric or non-parametric, as appropriate. We will also explore trends over time (e.g., decreasing for INR and increasing for pre-albumin) and estimate p-values via regression models using generalized estimating equations or random effects to account for within subject correlations. When describing outcomes over time, we will explore the effect of predictors of poor hepatic outcomes, such as use of antifungal agents (e.g., amphotericin) and antidiarrheal agents (e.g., loperamide), on potential spikes.

[name], Department of Surgery, Children's Hospital & Medical Center  
[name], Department of Surgery, Children's Hospital & Medical Center  
[name], Pediatric Research Office, Dept. of Pediatrics, UNMC  
[name], Department of Biostatistics, College of Public Health, UNMC

We will also evaluate nutritional outcomes including difference in weight-for- age Z-scores and height-for-age Z-scores from baseline to the moment in which the child starts enteral feeding and to the moment in which the child receives less than 10% of their calories from PN. Using linear regression, we will explore adjustment for baseline alternative predictors of interest. Trends over time in Z-scores will also be explored using regression with repeated measure methods.

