Assessment of efficacy will be also based on comparison of means (or medians) of the mean and maximum modified PELD scores of each subject across all follow-up weeks. Adjustments of these comparisons for potential confounders will be based on linear regression models. Mean rates of infection will be compared using logrank and Cox proportional hazards models.

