#### *Statistical Power and Sample Considerations*

The number of subjects included in the study will be based on a compassionate use protocol and not on study power considerations. The primary safety analysis will be descriptive and not based on statistical significance. However, in Table 4 we outline power to detect several differences in the frequency of adverse events, assuming 20, 25, or 30 patients, diverse proportion of subjects with adverse event in either treatment period and not with the adverse event in either treatment period and not with the adverse event in the other (proportion of discordant pairs), for a two-sided 5% significance level McNemar's tests.

For lower proportions of discordant pairs, we would generally attain close to 80% power in McNemar's test. Even for higher proportions of discordant pairs, assuming the high differences between before and after treatment that we expect to observe, e.g., 50% or more, 80% power can be attained in McNemar's test (Table 4).

Table 4—Power to detect varying differences in proportions before and after treatment with Omegaven® in a McNemar's test. All calculations based on an alpha significance level of 0.05

Difference between proportions	Proportion of discordant pairs	McNemar's Test		
		Sample Size		
		20	25	30
30%	40%	59%	72%	81%
	60%	44%	55%	63%
50%	60%	92%	97%	99%
	80%	79%	88%	93%
80%	85%	>99%	>99%	>99%
	95%	>99%	>99%	>99%

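### Infection outcomes are counts over follow-up time, but the logrank and Cox methods named to test them do not, in standard form, compare mean rates

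*Protocol*

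**What the plan says.** Under Treatment safety (section D, Outcome/Endpoints) the protocol lists a "rate of blood stream infections (number of positive blood cultures/follow-up-time under PN after baseline") and, for central venous catheter (CVC) infections, the "number of CVC infections/follow-up time and number of gram positive CVC infections/follow-up time". Both are event counts over time at risk, to which one child can contribute several events.

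Hypothesis 2.3 under Aim 2 is framed the same way: because of better immune function, Omegaven® patients are expected to do better, in that "they will have a lower infection rate than patients receiving conventional fat emulsions".

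The Analysis of Efficacy section ends with the test: "Mean rates of infection will be compared using logrank and Cox proportional hazards models". It does not say whether the time variable runs to the first infection or covers repeated ones, and it names no groups or periods.

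The Analysis of Safety and Tolerability section makes the primary safety analyses descriptive and adds significance tests as secondary, with paired tests for comparisons between periods. For trends over time it names "regression models using generalized estimating equations or random effects to account for within subject correlations". It does not name these models for infection counts.

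**The concern.** The outcome, the hypothesis and the words about mean rates all point to a rate in which every infection counts. The two named methods, as normally applied, answer a different question: how soon a first infection occurs. A change confined to repeat infections would be invisible to them.

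Repeat infections are plausible in this population. Children must be expected to need parenteral nutrition (PN) for at least another 30 days, they stay on Omegaven® until weaned, and the protocol itself lists blood stream infection, and re-hospitalization for it, among the expected adverse events.

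At stake is the formal test of hypothesis 2.3. Followed literally, it could show no difference although the stated outcome differs, or use only part of the infection data in what may be a small study. Because the protocol fixes both the endpoint and the method, this is a mismatch in its text and not merely a detail left to a statistical analysis plan.

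**Working it through.** **Plan's own figure.** There is none to reproduce. The protocol gives no infection rate, rate ratio, dispersion, event number or power for this comparison. Table 4 covers McNemar tests only.

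**Step 1: endpoint against method.**

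| Item | Where | What it targets |
|---|---|---|
| Blood stream and CVC infections | Treatment safety | Count over follow-up time, repeats included |
| Hypothesis 2.3 | Hypothesis for Aim 2 | Infection rate |
| Planned comparison | Analysis of Efficacy | Described as mean rates |
| Named methods | Analysis of Efficacy | In standard form, the hazard of a first event |

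The first three rows agree and the fourth does not. Nothing in the protocol bridges the gap: there is no time-to-first-infection endpoint, no recurrent-event form of the Cox model, and no count model with an offset.

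**Step 2: share of infections a first-event analysis would use (illustration).** Assume equal follow-up and a mean of m infections per child. The share is the probability of at least one infection divided by m.

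- Poisson counts: (1 − exp(−m))/m
  - m = 0.5: 0.787
  - m = 1: 0.632
  - m = 2: 0.432
  - m = 3: 0.317
- Negative binomial counts with dispersion 1: [1 − 1/(1 + m)]/m = 1/(1 + m)
  - m = 0.5: 0.667
  - m = 1: 0.500
  - m = 2: 0.333
  - m = 3: 0.250

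The values of m and the dispersion are assumptions.

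**Step 3: can the two targets disagree?** Let the first-infection hazard be h over one unit of time, and let the hazard after the first infection be k·h. With P = 1 − exp(−h), the mean count is P + k·h·(1 − P/h).

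- h = 1, P = 0.632
  - k = 0: 0.632
  - k = 1: 1.000
  - k = 3: 0.632 + 3 × 0.368 = 1.736
- h = 2, P = 0.865
  - k = 0: 0.865
  - k = 1: 2.000
  - k = 3: 4.271

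Two groups with the same h have a first-event hazard ratio of 1. Yet k = 0 against k = 3 gives mean counts that differ by 1.736/0.632 = 2.7-fold (h = 1) or 4.271/0.865 = 4.9-fold (h = 2). These are deliberately extreme cases. With k = 1 and children alike within each group, the first-event hazard ratio equals the rate ratio, and the only loss is precision.

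**The case against.** The strongest reply is that the protocol nowhere says that only first infections will be analysed. Cox models extend to recurrent events, a marginal version with robust variance does compare mean rates, and an analysis plan could name that version. This stands as far as it goes: a reader might infer that repeat infections are certain to be discarded, and the text does not establish that. It does not rescue the sentence, because no extension is named and the plain logrank test stands beside the Cox model.

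Second, repeat infections are not lost from the study. The outcome definitions count them, the primary safety analyses are descriptive, and the safety section allows paired tests between periods. This stands in full and confines the problem to the efficacy test.

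Third, the percentages are a property of a formula with an assumed mean and equal follow-up, whereas follow-up here varies with bilirubin response and weaning. This also stands; they are not an estimate of loss in this trial. Nor may one say that the cohort is 20 to 30 children: those are only the sizes assumed for Table 4, and the protocol states that "The number of subjects included in the study will be based on a compassionate use protocol and not on study power considerations".

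A reader might also carry over the rule that gives an infinite event time to children who die or are transplanted, which for infection would score death as the best result. That rule is introduced with a general phrase about survival analyses, but its content concerns bilirubin normalization, so the protocol does not support reading it into the infection analysis.

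**Conclusion.** The sentence is wrong as written: it promises a comparison of mean infection rates and names methods that, in standard form, compare first-infection hazards. That conclusion rests on the protocol's wording alone and needs no assumption about infection frequency.

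The consequence is modest. It touches the formal test behind hypothesis 2.3. It does not touch the primary safety outcomes (triene/tetraene ratio and INR), the primary efficacy outcome (time to bilirubin normalization) or any sample size calculation. As an illustration only, a first-event analysis would use 63%, 43% or 32% of infections at an assumed Poisson mean of 1, 2 or 3 per child with equal follow-up. The correction should be made, but the study's main conclusions do not depend on it.

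**What to change.** Replace the sentence in Analysis of Efficacy with a model for infection counts: either Poisson with robust variance and a small-sample correction, or negative binomial. Use the log of follow-up time as offset, taking time on PN after baseline as Treatment safety defines it for blood stream infections. That section says only follow-up time for CVC infections, so state that the same denominator applies or give another. Report rates per 1,000 days with 95% confidence intervals, and keep time to first infection (logrank and Cox) as a supporting analysis. Alternatively, name a recurrent-event Cox model with robust variance.

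The sentence should also name the groups or periods compared, since the design is a "non-randomized, open-labeled, prospective study of intravenously administered Omegaven® fat emulsion" and a new model does not supply a comparator. Clustering on child is needed only where a child contributes more than one period.

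The cost is a wording change and a little more analysis work. The counts and follow-up time are already required by the outcome definitions. Catheter-days are not listed among the data collected, so a rate per catheter-day would need a separate check. The downside is some dependence on the count model's variance assumption if the cohort is small.
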